12.3 Methods for Evaluation of Measurable Disease

All measurements should be taken and recorded in metric notation using a ruler or calipers. All baseline evaluations should be performed as closely as possible to the beginning of treatment and never more than 4 weeks before the beginning of the treatment.

The same method of assessment and the same technique should be used to characterize each identified and reported lesion at baseline and during follow-up. Imaging-based evaluation is preferred to evaluation by clinical examination unless the lesion(s) being followed cannot be imaged but are assessable by clinical exam.

Clinical lesions: Clinical lesions will only be considered measurable when they are superficial (e.g., skin nodules and palpable lymph nodes) and ≥ 10 mm diameter as assessed using calipers (e.g., skin nodules). In the case of skin lesions, documentation by color photography, including a ruler to estimate the size of the lesion, is recommended.

Chest x-ray: Lesions on chest x-ray are acceptable as measurable lesions when they are clearly defined and surrounded by aerated lung. However, CT is preferable.

Conventional CT and MRI: This guideline has defined measurability of lesions on CT scan based on the assumption that CT slice thickness is 5 mm or less. If CT scans have slice thickness greater than 5 mm, the minimum size for a measurable lesion should be twice the slice thickness. MRI is also acceptable in certain situations (e.g. for body scans).

Use of MRI remains a complex issue. MRI has excellent contrast, spatial, and temporal resolution; however, there are many image acquisition variables involved in MRI, which greatly impact image quality, lesion conspicuity, and measurement. Furthermore, the availability of MRI is variable globally. As with CT, if an MRI is performed, the technical specifications of the scanning sequences used should be optimized for the evaluation of the type and site of disease. Furthermore, as with CT, the modality used at follow-up should be the same as was used at baseline and the lesions should be measured/assessed on the same pulse sequence. It is beyond the scope of the RECIST guidelines to prescribe specific MRI pulse sequence parameters for all scanners, body parts, and diseases. Ideally, the same type of scanner should be used and the image acquisition protocol should be followed as closely as possible to prior scans. Body scans should be performed with breath-hold scanning techniques, if possible.

PET-CT: At present, the low dose or attenuation correction CT portion of a combined PET-CT is not always of optimal diagnostic CT quality for use with RECIST measurements. However, if the site can document that the CT performed as part of a PET-CT is of identical diagnostic quality to a diagnostic CT (with IV and oral contrast), then the CT portion of the PET-CT can be used for RECIST measurements and can be used interchangeably with conventional CT in accurately measuring cancer lesions over time. Note, however, that the PET portion of the CT introduces additional data which may bias an investigator if it is not routinely or serially performed.

Ultrasound: Ultrasound is not useful in assessment of lesion size and should not be used as a method of measurement. Ultrasound examinations cannot be reproduced in their entirety for independent review at a later date and, because they are operator dependent, it cannot be guaranteed that the same technique and measurements will be taken from one assessment to the next. If new lesions are identified by ultrasound in the course of the study, confirmation by CT or MRI is advised. If there is concern about radiation exposure at CT, MRI may be used instead of CT in selected instances.

Endoscopy, Laparoscopy: The utilization of these techniques for objective tumor evaluation is not advised. However, such techniques may be useful to confirm complete pathological response when biopsies are obtained or to determine relapse in trials where

recurrence following complete response (CR) or surgical resection is an endpoint.

Tumor markers: Tumor markers alone cannot be used to assess response. If markers are initially above the upper normal limit, they must normalize for a patient to be considered in complete clinical response. Specific guidelines for both CA-125 response (in recurrent ovarian cancer) and PSA response (in recurrent prostate cancer) have been published [JNCI 96:487-488, 2004; J Clin Oncol 17, 3461-3467, 1999; J Clin Oncol 26:1148-1159, 2008]. In addition, the Gynecologic Cancer Intergroup has developed CA-125 progression criteria which are to be integrated with objective tumor assessment for use in first-line trials in ovarian cancer [JNCI 92:1534-1535, 2000].

Cytology, Histology: These techniques can be used to differentiate between partial responses (PR) and complete responses (CR) in rare cases (e.g., residual lesions in tumor types, such as germ cell tumors, where known residual benign tumors can remain).

The cytological confirmation of the neoplastic origin of any effusion that appears or worsens during treatment when the measurable tumor has met criteria for response or stable disease is mandatory to differentiate between response or stable disease (an effusion may be a side effect of the treatment) and progressive disease.

FDG-PET: While FDG-PET response assessments need additional study, it is sometimes reasonable to incorporate the use of FDG-PET scanning to complement CT scanning in assessment of progression (particularly possible 'new' disease). New lesions on the basis of FDG-PET imaging can be identified according to the following algorithm:

- Negative FDG-PET at baseline, with a positive FDG-PET at follow-up is a sign of PD based on a new lesion.
- No FDG-PET at baseline and a positive FDG-PET at follow-up: If the positive FDG-PET at follow-up corresponds to a new site of disease confirmed by CT, this is PD. If the positive FDG-PET at follow-up is not confirmed as a new site of disease on CT, additional follow-up CT scans are needed to determine if there is truly progression occurring at that site (if so, the date of PD will be the date of the initial abnormal FDG-PET scan). If the positive FDG-PET at follow-up corresponds to a pre-existing site of disease on CT that is not progressing on the basis of the anatomic images, this is not PD.
- FDG-PET may be used to upgrade a response to a CR in a manner similar to a biopsy in cases where a residual radiographic abnormality is thought to represent fibrosis or scarring. The use of FDG-PET in this circumstance should be prospectively described in the protocol and supported by disease-specific medical literature for the indication. However, it must be acknowledged that both approaches may lead to false positive CR due to limitations of FDG-PET and biopsy resolution/sensitivity.

Note: A 'positive' FDG-PET scan lesion means one which is FDG avid with an uptake greater than twice that of the surrounding tissue on the attenuation corrected image.

12.4 Response Criteria

12.4.1 Evaluation of Target Lesions

Complete Response (CR): Disappearance of all target lesions. Any pathological lymph nodes (whether target or non-target) must have reduction in short axis to <10 mm.

Partial Response (PR): At least a 30% decrease in the sum of the diameters of target lesions, taking as reference the baseline sum diameters.

Progressive Disease (PD): At least a 20% increase in the sum of the diameters of target lesions, taking as reference the smallest sum on study (this includes the baseline sum if that is the smallest on study). In addition to the relative increase of 20%, the sum must also demonstrate an absolute increase of at least 5 mm. (Note: the appearance of one or more new lesions is also considered progressions).

Stable Disease (SD): Neither sufficient shrinkage to qualify for PR nor sufficient increase to qualify for PD, taking as reference the smallest sum diameters while on study.

12.4.2 Evaluation of Non-Target Lesions

Complete Response (CR): Disappearance of all non-target lesions and normalization of tumor marker level. All lymph nodes must be non-pathological in size (<10 mm short axis).

Note: If tumor markers are initially above the upper normal limit, they must normalize for a patient to be considered in complete clinical response.

Non-CR/Non-PD: Persistence of one or more non-target lesion(s) and/or maintenance of tumor marker level above the normal limits.

Progressive Disease (PD): Appearance of one or more new lesions and/or unequivocal progression of existing non-target lesions. Unequivocal progression should not normally trump target lesion status. It must be representative of overall disease status change, not a single lesion increase.

Although a clear progression of “non-target” lesions only is exceptional, the opinion of the treating physician should prevail in such circumstances, and the progression status should be confirmed at a later time by the review panel (or Principal Investigator).

12.4.3 Evaluation of Best Overall Response

The best overall response is the best response recorded from the start of the treatment until disease progression/recurrence (taking as reference for progressive disease the smallest measurements recorded since the treatment started). The patient's best response assignment will depend on the achievement of both measurement and confirmation criteria.

For Patients with Measurable Disease (i.e., Target Disease)

Target Lesions	Non-Target Lesions	New Lesions	Overall Response	Best Overall Response when Confirmation is Required*
CR	CR	No	CR	>4 wks. Confirmation**
CR	Non-CR/Non-PD	No	PR	>4 wks. Confirmation**
CR	Not evaluated	No	PR	
PR	Non-CR/Non-PD/not evaluated	No	PR	
SD	Non-CR/Non-PD/not evaluated	No	SD	Documented at least once >4 wks. from baseline**
PD	Any	Yes or No	PD	no prior SD, PR or CR
Any	PD***	Yes or No	PD	
Any	Any	Yes	PD	

* See RECIST 1.1 manuscript for further details on what is evidence of a new lesion. ** Only for non-randomized trials with response as primary endpoint. *** In exceptional circumstances, unequivocal progression in non-target lesions may be accepted as disease progression. Note: Patients with a global deterioration of health status requiring discontinuation of treatment without objective evidence of disease progression at that time should be reported as “symptomatic deterioration.” Every effort should be made to document the objective progression even after discontinuation of treatment.
				

For Patients with Non-Measurable Disease (i.e., Non-Target Disease)

Non-Target Lesions	New Lesions	Overall Response
CR	No	CR
Non-CR/non-PD	No	Non-CR/non-PD*
Not all evaluated	No	not evaluated
Unequivocal PD	Yes or No	PD
Any	Yes	PD

* ‘Non-CR/non-PD’ is preferred over ‘stable disease’ for non-target disease since SD is increasingly used as an endpoint for assessment of efficacy in some trials so to assign this category when no lesions can be measured is not advised
		

12.4.4 Duration of Response

Duration of overall response: The duration of overall response is measured from the time measurement criteria are met for CR or PR (whichever is first recorded) until the first date that recurrent or progressive disease is objectively documented (taking as reference for progressive disease the smallest measurements recorded since the treatment started).

The duration of overall CR is measured from the time measurement criteria are first met for CR until the first date that progressive disease is objectively documented.

Duration of stable disease: Stable disease is measured from the start of the treatment until the criteria for progression are met, taking as reference the smallest measurements recorded since the treatment started, including the baseline measurements.

13.0 DATA AND SAFETY MONITORING

In compliance with the Washington University Institutional Data and Safety Monitoring Plan, the Principal Investigator will provide a Data and Safety Monitoring (DSM) report to the Washington University Quality Assurance and Safety Monitoring Committee (QASMC) semi-annually beginning six months after accrual has opened (if at least five patients have been enrolled) or one year after accrual has opened (if fewer than five patients have been enrolled at the six-month mark).

The Principal Investigator will review all patient data at least monthly and provide a semi-annual report to the Quality Assurance and Safety Monitoring Committee (QASMC). This report will include:

- HRPO protocol number, protocol title, Principal Investigator name, data coordinator name, regulatory coordinator name, and statistician
- Date of initial HRPO approval, date of most recent consent HRPO approval/revision, date of HRPO expiration, date of most recent QA audit, study status, and phase of study
- History of study including summary of substantive amendments; summary of accrual suspensions including start/stop dates and reason; and summary of protocol exceptions, error, or breach of confidentiality including start/stop dates and reason
- Study-wide target accrual and study-wide actual accrual
- Protocol activation date
- Average rate of accrual observed in year 1, year 2, and subsequent years
- Expected accrual end date
- Objectives of protocol with supporting data and list the number of participants who have met each objective
- Early stopping rules with supporting data and list the number of participants who have met the early stopping rules
- Summary of toxicities
- Abstract submissions/publications
- Summary of any recent literature that may affect the safety or ethics of the study

The study principal investigator and Research Patient Coordinator will monitor for serious toxicities on an ongoing basis. Once the principal investigator or Research Patient Coordinator becomes aware of an adverse event, the AE will be reported to the HRPO and QASMC according to institutional guidelines.

14.0 STATISTICAL CONSIDERATIONS

14.1 Study Design

This is an open label, single-arm phase II trial focusing on the response rate of the therapeutic agent. Since this is a study in patients with specifically targeted mutations, a rather big treatment effect size is expected. Based on historical data, we assume a null hypothesis of an overall response rate of <1% in this setting.⁹ We hypothesize that an overall response rate of 30% or higher warrants further investigation. A total of N=12 patients will be enrolled for this study, based on the exact single-stage design with 85% power at a 1-sided 0.05 significance level (using *ph2single* function from library *clinfun* in the R package). If 2 or more responders are observed out of these 12 patients, we would conclude that preliminary evidence for efficacy exists and that further investigation of the treatment is warranted.

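### Section 14.1 gives 85% power for N=12, but its own rule of 2 or more responders has exact power 91.5% at a 30% response rate (minor, conservative)

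*Combined protocol and SAP*

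**What the plan says.** All the design inputs are in Section 14.1 (Study Design):

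- Null: "we assume a null hypothesis of an overall response rate of <1% in this setting".
- Rate of interest: "We hypothesize that an overall response rate of 30% or higher warrants further investigation".
- Size and nominal error rates: "N=12 patients will be enrolled for this study, based on the exact single-stage design with 85% power at a 1-sided 0.05 significance level".
- Decision rule: "If 2 or more responders are observed out of these 12 patients", the treatment is judged to merit further study.

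The section names the R function that was used. It does not give the attained power or the attained type I error, does not call 85% a minimum, and makes no allowance for patients who cannot be assessed. No other section restates the power.

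**The concern.** For a single-stage exact design, the sample size, the cut-off and the alternative response rate determine the power completely. Section 14.1 gives all three, and together they do not produce 85%. The null rate, which is given only as below 1%, plays no part in the power, so it cannot explain the gap.

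What is at stake is how a negative result is read. If 0 or 1 of the 12 patients respond, the power tells the reader how often a drug with a true 30% response rate would be missed. A reader who relies on 85% puts that at 15%; the rule as written gives 8.5%. This is the plan's only power statement.

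**Working it through.** **Inputs, all from Section 14.1.** n = 12; success if the number of responders X is 2 or more; alternative rate 30%; null below 1%, taken at its upper boundary of 1%; one-sided level 0.05; exact binomial, single stage.

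**Step 1. Try to reproduce the stated 85%.**

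P(X ≥ 2 | n, p) = 1 − (1−p)^n − n·p·(1−p)^(n−1)

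With n = 12 and p = 0.30:

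- 0.7^12 = 0.0138
- 12 × 0.3 × 0.7^11 = 0.0712
- power = 1 − 0.0138 − 0.0712 = 0.9150
- type II error = 0.0850

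The stated figure is not reproduced. The gap is 91.5 − 85 = 6.5 percentage points.

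**Step 2. Type I error of the same rule.** With p = 0.01, P(X ≥ 2 | n = 12) = 0.0062, well inside 0.05.

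**Step 3. Could another cut-off at n = 12 be meant?**

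| Cut-off | Type I error at 1% | Power at 30% |
|---|---|---|
| 1 or more | 0.1136 | 98.6% |
| 2 or more | 0.0062 | 91.5% |
| 3 or more | 0.0002 | 74.7% |

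None gives 85%, and a cut-off of 1 breaks the 0.05 limit at a 1% null.

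**Step 4. Which sample size does give 85%?** Null 1%, rule of 2 or more:

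| n | Type I error at 1% | Power at 30% |
|---|---|---|
| 9 | 0.0034 | 80.4% |
| 10 | 0.0043 | 85.07% |
| 11 | 0.0052 | 88.7% |
| 12 | 0.0062 | 91.5% |

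A cut-off of 1 does not give a smaller qualifying design: n = 5 has type I error 0.0490 but power of only 83.2%, and from n = 6 the type I error exceeds 0.05 (0.0585 at n = 6). At a 1% null, the smallest exact design with at least 85% power is therefore n = 10, and the smallest with at least 90% is n = 12. This comparison depends on the null being set at 1%; Step 1 does not.

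**Step 5. At what true rate does the 12-patient rule have 85% power?** Solving P(X ≥ 2 | 12, p) = 0.85 gives p = 0.2546, about 25.5%, which is below the stated 30%.

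**Step 6. Could a normal approximation explain it?** No. With the same rates and error levels it gives n of about 4.8, or 5 patients, and Section 14.1 says that the design is exact.

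**The case against.** The strongest reply is that 85% and 0.05 stand in the same clause and should be read alike. An exact binomial design is discrete and can rarely hit either target, so both figures are naturally requirements: a floor for power and a ceiling for type I error. On that reading the design meets both, since 91.5% is at least 85% and 0.6% is at most 5%. The sample size is also said to be based on that specification, which need not be a report of attained values. This stands so far as 85% is true as a floor. It does not reconcile the text, because a floor of 85% leads to 10 patients at a 1% null, and the choice of 12 is left unexplained.

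A second reply is that 91.5% assumes that every enrolled patient has a 30% chance of being counted as a responder. Response depends on the follow-up scan at 8 weeks (Section 5.0) and on a confirmatory scan (Sections 12.1 and 12.4.3). If 30% applies only to assessable patients, then one unassessable patient among the 12 lowers the power of the same rule to 88.7%, and two lower it to 85.07%. Two spare patients would thus account for the stated figure. This is a fair caution about the condition attached to 91.5%. However, Section 14.1 states no such allowance and applies the rule to all 12 patients, so it cannot be taken as the plan's reasoning.

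A third reply is that nothing in the conduct of the trial changes. That is correct, and it sets the severity: the analysis in Section 14.2, a response rate with a 90% confidence interval, does not use the power figure.

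**Conclusion.** The concern holds: the power is wrong as written, but the error is minor and conservative. The stated rule has power 91.5% at a 30% response rate, against 85% stated. A reader who takes 85% at face value overstates the chance of missing a true 30% rate by a factor of 15/8.5, or about 1.8. The trial is not underpowered, and the sample size, the decision rule, control of type I error and the conclusion drawn from the rule are unaffected.

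The 91.5% rests on the 30% rate applying to all 12 enrolled patients, which is how Section 14.1 frames the rule. The attained type I error of 0.6% rests on taking the null at 1%; a lower null would make it smaller. Whether 85% was meant as a minimum or as the attained power cannot be told from the text.

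**What to change.** Keep N=12 and the rule. In Section 14.1, replace the power clause with the attained values: exact power 91.5% at a 30% response rate in all enrolled patients (at least 85% required); attained one-sided type I error 0.6% at a 1% response rate (nominal limit 0.05).

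If two of the 12 patients were meant as a margin for patients who cannot be assessed, say so, and give the 85.07% power that 10 assessable patients provide.

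The cost is one sentence, or two if the margin is described. No extra patients, data or design change are needed.

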14.2 Data Analysis

The primary endpoint will be to describe the response rate using RECIST 1.1. Response rate will be defined as complete response (disappearance of all target lesion) plus partial response (a least a 30% decrease in the sum of diameters of target lesions). Secondary endpoint will be to further evaluate molecular markers of response or resistance using exome sequencing and transcriptome sequencing when feasible.

Demographic and clinical characteristics of the sample, as well as response, and toxicity by grade will be summarized using descriptive statistics. The overall response rate and its 90% confidence interval will be estimated. If possible, permutation tests will also be performed to compare the differences of secondary endpoints between responders and non-responders. The distribution associated with no difference (the null distribution) can be identified using the data in hand. If there is no difference between the values seen in responders and those in non-responders, then, for this purpose, it does not matter whether a given patient is labeled as a responder or a nonresponder. So we can randomly shuffle the response labels and calculate the test statistic from the shuffled data. If this procedure is repeated 10,000 times, the resulting 10,000 test statistics provide an accurate representation of the null distribution. The observed test statistic, based on patients assigned to the correct response group, is then compared to the null distribution. If the observed test statistic is unusually large or small, so very few values from the null distribution are larger or smaller than the observed test statistic, then the observed difference between responders and non-responders is unlikely if the null hypothesis were correct. In that case, we can reject the null hypothesis of no difference and conclude that there is a true difference between responders and non-responders. Then the null distribution

of the test statistics will be generated by simulating 10,000 datasets where the status of response was randomly shuffled. In order to quantify the extent to which the observed test statistic is “unusual,” a permutation test generates a p-value, which is equal to the proportion of test statistics from the label-shuffled samples that exceed the observed test statistics.

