2.0 OBJECTIVES

2.1 Primary Objectives

To assess the response rate of patients with solid malignancies whose tumors carry mutations in TSC1, TSC2, NF1, NF2, or STK11 to everolimus.

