3.0 PATIENT SELECTION

3.1 Inclusion Criteria

1. Histologically confirmed diagnosis of advanced (metastatic, recurrent, or unresectable) cancer with mutations in any of the following genes: TSC1, TSC2, NF1, NF2 or STK11
2. Must have failed at least 1 standard of care systemic therapy for their malignancy.
3. Measurable disease defined as lesions that can be accurately measured in at least one dimension (longest diameter to be recorded) as ≥ 10 mm with CT scan, as ≥ 20 mm by chest x-ray, or ≥ 10 mm with calipers by clinical exam.
4. Prior therapy (chemotherapy, radiation therapy, and surgery) is allowed if completed at least 2 weeks prior to registration and if all treatment-related toxicities are resolved to \leq CTCAE grade 1, with the exception of alopecia and hematologic values otherwise meeting the bone marrow function criteria specified below.
5. At least 18 years of age.
6. ECOG performance status ≤ 2 (see Appendix A).
7. Normal bone marrow and organ function as defined below:
 - a. Leukocytes $> 3,000/\text{mcL}$
 - b. Absolute neutrophil count $> 1,500/\text{mcL}$
 - c. Platelets $> 100,000/\text{mcL}$
 - d. Hemoglobin > 9.0 g/dL
 - e. Total serum bilirubin ≤ 2.0 x IULN
 - f. AST(SGOT)/ALT(SGPT) ≤ 2.5 x IULN (≤ 5.0 x IULN in patients with liver metastases)

- g. Serum creatinine $\leq 1.5 \times$ IULN OR creatinine clearance > 45 mL/min/1.73 m² for patients with creatinine levels above institutional normal
 - h. Fasting cholesterol ≤ 300 mg/dL OR ≤ 7.75 mmol/L AND fasting triglycerides $\leq 2.5 \times$ IULN. NOTE: In case one or both of these thresholds are exceeded, the patient can only be included after initiation of appropriate lipid lowering medication
8. Able to swallow tablets.
 9. Women of childbearing potential, defined as all women physiologically capable of becoming pregnant, must use highly effective methods of contraception (please refer to Section 5.4) during the study and for 8 weeks after. Women are considered post-menopausal and not of childbearing potential if they have had 12 months of natural (spontaneous) amenorrhea with an appropriate clinical profile (e.g., age appropriate, history of vasomotor symptoms) or have had surgical bilateral oophorectomy (with or without hysterectomy) or tubal ligation at least six weeks prior to randomization. In the case of oophorectomy alone, only when the reproductive status of the woman has been confirmed by follow-up hormone level assessment is she considered not of childbearing potential.

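### The responder comparison in section 14.2 ignores tumor type, so if responders cluster in one type, tissue-of-origin genes can be reported as markers of everolimus response (minor; exploratory analysis only)

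*Combined protocol and SAP*

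**What the plan says.** The population is defined by gene, not by histology. Section 2.1 states the objective as "To assess the response rate of patients with solid malignancies whose tumors carry mutations in TSC1, TSC2, NF1, NF2, or STK11", and item 1 of section 3.1 admits a "Histologically confirmed diagnosis of advanced (metastatic, recurrent, or unresectable) cancer with mutations in any of the following genes: TSC1, TSC2, NF1, NF2 or STK11". No section sets a cap, quota or stratum by tumor type. Section 14.1 fixes the size: "A total of N=12 patients will be enrolled for this study".

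Section 14.2 gives the secondary endpoint as to "further evaluate molecular markers of response or resistance using exome sequencing and transcriptome sequencing when feasible". It then plans, where feasible, to compare responders with non-responders by permutation: "So we can randomly shuffle the response labels and calculate the test statistic from the shuffled data". This is done 10,000 times over the whole sample. An unusually extreme statistic leads to the conclusion that the two groups really differ. Clinical characteristics are summarized descriptively. Nothing in section 14.2 or elsewhere blocks the shuffle by tumor type, adjusts for it, or limits how a significant marker may be interpreted.

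**The concern.** Free shuffling is justified in section 14.2 by the argument that, without a difference, it does not matter which patient carries which label. That suffices for the literal null that the two groups have the same distribution. It does not suffice for a claim about markers of response. If both response and gene expression vary with tissue of origin, the groups will differ on genes that have no relation to response within any tumor type.

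This is confounding rather than chance. It can affect a single gene chosen in advance, and multiplicity control does not remove it. At stake is the interpretation of the exome and transcriptome comparison: a tissue marker could be reported as a marker of everolimus response or resistance, and follow-up work could pursue it.

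**Working it through.** **The plan's own figure.** Section 14.1 gives N=12, success at 2 or more responders, null rate below 1% (0.01 used here), target rate 30%, 85% power and one-sided 0.05. By exact binomial:

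- Power: 1 − 0.7^12 − 12(0.3)(0.7^11) = 0.915.
- Type I error: 1 − 0.99^12 − 12(0.01)(0.99^11) = 0.0062.

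Both stated constraints are met. The relevance here is that at the target rate 2 or more responders occur 91.5% of the time. The plan states no figure for the permutation test.

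**Can a tissue gene reach 0.05?** With r responders among 12 patients there are C(12, r) labelings: 12, 66, 220 and 495 for r = 1 to 4. The smallest one-sided p-values are 1/12 = 0.083, 1/66 = 0.015, 1/220 = 0.0045 and 1/495 = 0.0020. From two responders on, it can. If all r responders lie in a type of m patients and the gene separates that type clearly from the rest, the one-sided p is at most C(m, r)/C(12, r):

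- 2 of 3: 3/66 = 0.045.
- 3 of 4: 4/220 = 0.018.

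**How often does it?** The following are assumptions, because the documents give none of them: the tumor mix, a gene shifted by 3 within-type standard deviations (SD) in type A and unrelated to response within type, the absolute mean difference as statistic, a two-sided test with ties counted, and a 0.05 cut-off. All labelings were enumerated on simulated genes.

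| Responders | Unrestricted shuffle, p<=0.05 |
|---|---|
| 2 of 3 in type A, none elsewhere | about 70% |
| 3 of 4 in type A, none elsewhere | about 82–84% |
| 2 of 6 in type A, none elsewhere | about 9–10% |
| 2 of 3 in type A, one elsewhere | about 24% |
| 2 of 4 in type A, one elsewhere | about 7–8% |
| 1 of 4 in type A, one elsewhere | under 1% |
| Any of the first three patterns, no tissue shift | about 4–5% |

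At shifts of 2 and 4 SD, the 2-of-3 pattern gives 42% and 88%, and the 3-of-4 pattern gives 55% and 96%.

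Averaging over random response, with 4 type A patients, 8 others, a 3 SD shift and at least two responders:

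- Response 70% in type A and 10% elsewhere: about 49% unrestricted and 2% within type.
- Response 30% in both: about 5% unrestricted.

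**What can a within-type shuffle do?** When all responders are in type A, its smallest p is 1/C(m, r): 1/3 = 0.33 for 2 of 3, 1/4 = 0.25 for 3 of 4, and 1.0 if the whole type responds. More generally, at a 30% response rate the share of trials in which it can reach 0.05 at all is:

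- 0% with 12 different types.
- About 5% with six types of 2. A pair is mixed with probability 2(0.3)(0.7) = 0.42, and at least five mixed pairs are needed because 2^5 = 32 exceeds 20: 6(0.42^5)(0.58) + 0.42^6 = 0.051.
- 45% to 67% with three or four types.

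**The case against.** The strongest reply is that the high rates belong to a chosen outcome: every responder in one type, and nearly all of that type responding. The documents give no tumor mix and no response rates by type, and section 14.1 attributes the expected effect to the mutations. If response does not depend on type, the test behaves as intended. This stands. The risk is conditional, and one responder outside the cluster can cut it sharply.

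Second, the test is valid for the null it states: a tissue gene concentrated in the responders is a real difference between the groups. This also stands. The fault lies in reading that difference as a marker of response, and section 14.2 contains nothing to prevent it.

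Third, a reader might infer that secondary objective 1 will be answered wrongly. The documents do not support that. Section 2.2 phrases that objective as the correlation of mTOR-pathway mutations with response, whereas the calculations concern a shift in expression. No effect on a mutation marker was shown. The transcriptome work is itself conditional on feasibility, and the section 10 calendar lists research tissue only at progression and archival tissue only for the five-gene test.

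Fourth, shuffling within tumor type cannot rescue the analysis. In the two patterns with the highest rates it cannot reject for any gene, true marker or not. This rules it out as a gate, but not as a sensitivity analysis.

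**Conclusion.** The point holds as a conditional weakness of an exploratory analysis. If responders cluster in one tumor type, genes that only mark that tissue can be reported as markers of everolimus response or resistance, because section 14.2 neither accounts for tumor type nor qualifies the conclusion. Under the stated assumptions the chance per such gene runs from about 70–84% in tight clusters, through about 9% when 2 of 6 respond, to about 5% when response is unrelated to type.

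A reader might go further and infer that every gene specific to the responders' tissue will be declared a marker. Neither the documents nor the figures support that: the bounds of 3/66 and 4/220 need clear separation between tissues, and nothing in the documents says that responders will cluster. The primary response rate and the rule of 2 or more responders are untouched. Severity: minor.

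**What to change.** Keep the unrestricted test and add to section 14.2:

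1. Tumor type and mutated gene will be listed by patient beside each marker result.
2. Where a tumor type contains both responders and non-responders, the shuffle will be repeated within tumor type as a sensitivity analysis, and the smallest p-value it could have reached will be stated.
3. When the responders are concentrated in one tumor type and the marker tracks that type, the difference will be reported as not separable from tumor type, and not as a marker of response or resistance.
4. A marker will not be ruled out only because the within-type shuffle fails to reject, since with 12 patients it often cannot reach 0.05.

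The cost is a few sentences and one further run of the same analysis. The downside is fewer firm marker claims, and in some outcomes none.
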